Hypothesis 3: The use of both BoNT-A injections and supervised gait retraining will be more effective than either treatment alone. In adult active duty service members with CECS, the use of both BoNT-A injections and supervised gait retraining returns service members to full duty, including being able to complete their service-specific military physical tests, sooner and for sustained longer periods than SGR or BoNT-A injections alone.

Process for Hypothesis 3: Evaluate functional improvements in Group 4 as compared to Groups 2 & 3 via the subjective and objective data variables described in protocol sections 10.1 & 10.2. Assess the ability of all study groups to complete a 2-mile run and to compete their required service-specific physical fitness testing within the established standards at 8 weeks, 3 months, 6 months, and 12 months post-study injection.

9.4 Study Design:

Describe study design in one to two sentences (e.g., prospective, use of existing records/data /specimens, observational, cross-sectional, interventional, randomized, placebo-controlled, cohort, etc.). Specify the phase – Phase I, II, III, or IV – for FDA-regulated investigational drug research

Multi-site, single-blinded randomized placebo-controlled study

9.5 Target Population:

Describe the population to whom the study findings will be generalized

Adult military beneficiaries diagnosed with Chronic Exertional Compartment Syndrome (CECS)

9.6 Benefit to the DoD:

State how this study will impact or be of benefit to the Department of Defense

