Those randomized into a BoNT-A injections group (i.e., Group 3 or 4) will receive up to 2 injections per affected anterior and/or lateral compartment. Per standard clinical procedure, a solution of 25 units of Botulinum toxin, per 1 mL of normal saline will be used for each injection. Standard aseptic technique will be followed. Insertion into the correct compartment will be accomplished using ultrasound guidance. The anterior and/or lateral compartments will each be separated into thirds measuring from the tibial plateau to the head of the calcaneus. Injections will be given at approximately 1/3 the distance from the tibial plateau for the proximal injection and 2/3 the distance from the tibial plateau for the distal injection. Injections will only be given in the compartments that have elevated compartment pressure using the standard Pedowitz criteria: 1) a pre-exercise pressure greater than or equal to 15 mmHg, 2) a 1 minute post-exercise pressure of greater than or equal to 30 mmHg, or 3) a 5 minute post-exercise pressure greater than or equal to 20 mmHg.¹² If the lateral compartment is affected, a total of 50 units of botulinum toxin will be given. The proximal aspect of the peroneus longus and brevis is approximately 1/3 the distance from the tibial plateau and it will receive 25 units of botulinum toxin A. The distal aspect of the peroneus longus and brevis is approximately 2/3 the distance from the tibial plateau and this area will also receive 25 units of botulinum toxin A. If the anterior compartment is affected, a total of 50 units of botulinum toxin will be given; 25 units to the proximal anterior compartment and 25 units to the distal anterior compartment.^{1,2}

Of note, CECS mainly affects the anterior and lateral compartments and is rarely seen in the superficial posterior or deep posterior areas; thus, the anterior and lateral compartments will be the focus of this study and patients with concomitant or isolated posterior compartment symptoms will not be included in this study. Participants who receive BoNT-A injections will be provided with a Post-Injection After Care Handout (Appendix O). The information provided to the participant after the injection are observed signs and/or symptoms that could occur with receiving either a BoNT-A or saline injection. This handout is not likely to expose the blinding of the injection that the participant receives as part of the study.

Saline Injections:

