Those randomized into the normal saline groups will receive injections in the identical manner above, using the appropriate amount of solution (0.5 mL to 1 mL). The syringes will be prepared by the clinical research staff using standard sterile techniques, out of view of the participant to ensure appropriate blinding.

Study Injection Documentation (both groups):

All injections will be done under ultrasound guidance. The provider will use the ultrasound machine to identify bony landmarks of the tibial plateau and will then move the probe laterally towards the fibular head to identify the anterior and lateral compartments of the lower leg. Distally, the provider will identify the midway area between the fibular head and the tip of the lateral malleolus.

Study injection administration to the participant will be documented using a Treatment Documentation CRF (Appendix N). This Treatment Documentation CRF will be entered into REDCap. Study injection administration will also be documented in the participant's electronic medical record following standard procedures.

Supervised Gait Retraining (SGR):

The SGR course will focus on mid-forefoot strike, increasing their cadence while shortening their stride, and decreasing their peak ground reaction force. This program has been developed by physical therapists at West Point and the Army DPT program in Fort Sam Houston. This program uses group physical therapy sessions, lower extremity exercises, home exercise training drills, and advanced wearable technology to effectively change key gait parameters.

Supervised physical therapy sessions will be documented using a SGR Physical Therapy Documentation CRF (Appendix M). This SGR Physical Therapy Documentation CRF will be entered into REDCap. Study supervised physical therapy sessions will also be documented in the participant's electronic medical record following standard procedures. Participants in the SGR group(s) will also be sent home with a handout (Appendix L) explaining exercises that can/should be done from home to supplement their supervised physical therapy sessions.

Home Based Gait Retraining:

The HBGR will focus on increasing cadence, running softer and increasing endurance strength with exercises for the lower extremity. A handout (Appendix L) explaining desired exercises and gait retraining will be given to each participant with daily exercise instructions. Participants will be contacted weekly as a reminder to complete their home program.

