If the participant has a change of duty station (permanent or temporary) and/or cannot make an in-person visit, the following will be collected using Appendix E, Follow Up Data Collection Sheet: relevant medical and service history and demographic questions including age, gender, body mass index, symptoms duration, location, and characteristics, treatment history, work status, military rank, branch of service, length of service, limited duty/profile days, occupational specialty, concomitant medical conditions, activities provoking symptoms, location of symptoms, footwear characteristics and orthosis use, etc., numeric pain rating scale (NPRS), University of Wisconsin Running Injury and Recovery Index (UWRI), Single Assessment Numerical Evaluation (SANE), Patient Specific Functional Scale (PSFS) will also be assessed. This may be collected with electronic mail, postal mail, and/or telephone communication with the participant.

Many of the activities in this study are performed regularly as part of standard of care for patients being seen for lower extremity CECS. Please see Appendix H: Data Collection Schedule for details on which activities are standard of care.

Study Completion:

Participants' study completion or withdrawal will be documented on the Study Completion CRF (see Appendix S).

Additional Considerations - COVID-19:

For as long as deemed clinically appropriate, there will be additional precautions in place to ensure the health and safety of research staff and research participants and to combat the spread of COVID-19. Research staff will closely follow all current local clinical guidelines regarding the use of PPE, hand washing, disinfecting of equipment, proper distancing, etc. Additionally, the study team will reduce the need for in-person research-specific visits when possible. For participants assigned to one of Standardized Gait Retraining (SGR) groups, some of their clinical follow ups during the physical therapy period may be conducted and documented as a video/telehealth encounter. For participants assigned in all groups, the 24-month follow up visit which requires no physical examination can be conducted remotely, meaning the participants can complete the questionnaires electronically, over the phone, or hard copy via mail all while remaining at home.

Study Blinding:

Participants will be blinded to assigned treatment arm (i.e., saline vs. BoNT-A injection) until 3 months post-injection.

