The potential side effects of Botulinum toxin A injections include: rare minor side effects of bleeding, pain, soreness, infection, transient general muscle weakness and muscular atrophy, flu-like symptoms, and even rarer transient breathing and swallowing difficulties which has the potential to cause death if not appropriately treated.

The potential side effects of saline injections include: pain, soreness, bleeding, and infection which are all very rare.

The potential side effects of IMCP needle insertion for intramuscular compartment pressure testing include: pain which is minimized with local anesthesia, soreness, minor local bleeding, and the rare incidence of infection.

The potential risks for balance screening, physical objective measurements, physical performance based testing, gait retraining, standard gait analysis, self-paced treadmill test, and lower strengthening and stretching exercises include: physical discomfort (increased pain and reduced activity level), soreness, possible chronic or acute musculoskeletal injury, overuse or a fall.

Any time information is collected for a study, there is a small risk of breach of confidentiality.

14.2

Measures to Minimize Risks of Harm (Precautions, safeguards):

For each research procedure or intervention, describe all measures to minimize and/or eliminate risk of harms to subjects and study personnel

All available precautions will be taken to minimize the above-mentioned risks. Standard clinic protocols will be followed to reduce the risks of infections and related complications.

To minimize the risk to participants, once they receive their injection, a waiting period of at least 15 minutes will occur at the clinic. This waiting period is to observe for any side effects that may occur due to the injection. The participant will also be given an after care injection handout. In order to safeguard participants, providers will use ultrasound guidance to identify the locations of the anterior and lateral compartments of the lower leg. Expected soreness may occur from the study injection procedures which may impact the start of physical therapy visits to 2 weeks post injection. Providers will be trained on all study procedures. All of this will provide consistent delivery of treatment to the targeted areas and minimize risk to the participant.

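### Section 10.1 assigns the after-care handout to BoNT-A recipients and section 14.2 to any injected participant; followed literally, 10.1 would let receipt of the sheet track the blinded injection

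*Combined protocol and SAP*

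**What the plan says.** Three parts of section 10.1 and one part of section 14.2 bear on this.

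- **Section 10.1, BoNT-A Injections:** "Participants who receive BoNT-A injections will be provided with a Post-Injection After Care Handout (Appendix O". The next sentence says the handout describes "observed signs and/or symptoms that could occur with receiving either a BoNT-A or saline injection". The one after adds: "This handout is not likely to expose the blinding of the injection that the participant receives as part of the study".
- **Section 10.1, Saline Injections:** "Those randomized into the normal saline groups will receive injections in the identical manner above". The handout is not mentioned.
- **Section 10.1, Study Injection Documentation (both groups):** ultrasound guidance and record keeping are covered. The handout is not mentioned.
- **Section 14.2:** after a post-injection wait of at least 15 minutes in the clinic, "The participant will also be given an after care injection handout". Nothing restricts this by arm.

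Section 9.4 describes the design as "Multi-site, single-blinded randomized placebo-controlled study". Study Blinding in 10.1 says who is blinded and for how long: "Participants will be blinded to assigned treatment arm (i.e., saline vs. BoNT-A injection) until 3 months post-injection".

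**The concern.** When a placebo is given by injection, everything that accompanies the injection should be the same in both arms. Read literally, section 10.1 attaches a piece of paper to one arm. Receiving it would then carry information about allocation, however neutral its wording.

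What is at stake is the blinded part of follow-up. The blind is lifted once the 3-month visit is complete, so 8 weeks and 3 months are the only follow-ups at which participants are meant not to know their injection. They are also the only ones before participants may be offered an active treatment they did not receive. Section 10.2 lists eight primary outcome items. Four are patient-reported (UWRI, SANE, PSFS, GROC). A fifth, return to full active duty, depends partly on whether the patient finds the pain tolerable. The 2-mile run is tested on a self-paced treadmill, so it depends on effort. Such outcomes can respond to what a participant believes was injected.

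**Working it through.** No formula applies, and the plan gives no figure to reproduce. The check sets the passages side by side.

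1. **Does 10.1 restrict the handout?** The sentence sits under the BoNT-A heading and takes BoNT-A recipients as its subject. It does not contain the word only. The restriction comes from its subject and from the absence of a matching sentence for saline.

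2. **Does the saline paragraph import it?** That paragraph says saline injections are given in the same manner. This most naturally covers how the injection is performed, not what is handed over afterwards. Elsewhere 10.1 says so explicitly when it means both arms, for example in the timing rule for study injections under Randomization and in the instruction to all participants to avoid other therapy. A coordinator working from 10.1 could reasonably give the sheet to one arm.

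3. **Does 14.2 agree?** No. It speaks of the participant, after their injection, without naming an arm. A site working from 14.2 would give the sheet to everyone, so two sites could each follow the protocol and act differently.

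4. **Does the reassurance in 10.1 settle it?** It says the content suits either injection and concludes that the blind is unlikely to be exposed. That answers whether reading the sheet reveals the injection. It does not answer whether receiving it does.

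5. **What else must happen before a participant is unblinded?** The participant must learn or infer that those given the other injection get no sheet. Without that, neither a neutral sheet nor its absence says anything. Whether participants are told depends on Appendix O and the consent form, which were not available for this review.

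6. **Which outcomes are exposed?** Of the eight primary items in 10.2, five rest wholly or partly on patient judgement (four patient-reported scales + return to full duty = 5). All are due at 8 weeks and 3 months, within the blinded period.

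7. **Can the effect be sized?** No. The documents give no rate at which sheets would be withheld, noticed or discussed, and no effect of belief about treatment on any outcome.

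**The case against.** The strongest reply is that the handout was always meant for both arms. Its content is written for either injection, which would be odd for a sheet given to one arm. Its authors considered the blind expressly, and section 14.2 hands it to every injected participant. This largely stands. A reader might infer from 10.1 that a BoNT-A-only handout is settled procedure, but the documents show a conflict between two sections and no more. The reply does not remove the point, because 10.1 is where sites will look for injection procedures and its wording points the other way.

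The second reply is that unblinding needs participants to know what the other arm receives, and nothing available shows that they would. This also stands, and it limits how firmly the risk can be put.

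A reader might go further and argue that supervised gait retraining exposes the difference, since "This program uses group physical therapy sessions" and saline and BoNT-A participants (Groups 2 and 4) could meet there. The documents do not carry this far:

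- They give no group size and do not say that sessions consist only of trial participants.
- The handout is given in the injection clinic, while physical therapy starts 2 or more weeks later.
- Nothing says the sheet is brought along, and some supervised follow-up may be by telehealth.
- The stated test of BoNT-A (Hypothesis 1, section 9.3) compares Group 3 with Group 1. Both are home-based arms with a single in-person therapy session, so group sessions cannot reach that contrast.

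A reader might also infer that any bias would favour BoNT-A. That is plausible, but nothing in the documents allows the direction to be derived.

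**Conclusion.** Sections 10.1 and 14.2 disagree on who receives the after-care handout. Followed literally, 10.1 would make receipt track the assigned injection and could weaken the participant blind, the only one described, at the 8-week and 3-month visits for outcomes that patients judge themselves. Neutral content does not remove that risk.

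The conclusion rests on two conditions that cannot be checked here: that at least some sites follow 10.1 and not 14.2, and that participants come to know that the other arm gets no sheet. No size or direction of bias can be stated, and sample size and power are unaffected. Confidence is moderate. This is a cheap improvement to the wording, not evidence that the blind has failed.

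**What to change.** Reconcile 10.1 with 14.2. Take the handout sentence out of the BoNT-A paragraph and put it in the Study Injection Documentation (both groups) paragraph, worded along these lines: all participants, whichever study injection they receive, are given the same Post-Injection After Care Handout (Appendix O) after the injection. The two sentences on its content and on blinding should move with it. Section 14.2 can stay as it is.

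The cost is one reworded sentence and printing the existing sheet for the saline arms. As the protocol describes it, the content already suits either injection, so this change calls for no rewriting of the handout. The analysis does not change.

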Trade Drug Name:	Botox																											
Generic Drug Name:																												
Investigational Drug Name:																												
Identify the name of the manufacturer or source of investigational drug/biologic:	Allergan																											
Is the drug supplied at no cost?	Yes																											
Is the Drug FDA Approved:	Yes																											
Is this a new drug or a new use of an already approved drug	Yes																											
Is an IND necessary	No																											
IND Number																												
Who holds the IND:	N/A																											
IND details:	N/A - please see section below for exemption rationale.																											
If FDA Approved and an IND is not required, Please provide a rationale for exemption:	BotulinumtoxinA injections are already currently used in the sports medicine clinics at Fort Belvoir Community Hospital (FBCH) and the Uniformed Services University (USU) as well as in the Dept. of Physical Medicine & Rehabilitation (PM&R) at Walter Reed National Military Medical Center (WRNMMC) for the non-surgical treatment of CECS. Additionally, our use of BoNT-A in this study does not require an IND because it meets all of the required exemption criteria outlined by the FDA: 1) The drug we propose to use is currently lawfully marketed in the United States. 2) This study/investigation is not intended to be reported to the FDA as a well-controlled study. This study is also not intended to support neither a new indication of this drug nor a change to the current labeling of this drug. 3) This study does not intend to support a significant change in advertising for the drug. 4) Although this drug is not currently explicitly approved for the treatment of CECS, it is																											

	currently FDA approved for injection into extremity musculature for other medical conditions. We will be using this drug following a similar dosing guideline, using a similar route of administration, and in a population that it is already FDA approved for. Our intended procedures do not significantly increase the risks associated with the use of this drug. 5) This study will be conducted in compliance with the requirements for review by our IRB board. 6) This study is not intended to promote or commercialize this drug product.
Are you currently using this IND in another research project?	No
If yes, list the IRB Number(s):	N/A
Dose Range:	50-100 units per limb
Frequency:	one time

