Route of administration:	injection
Will the investigational pharmacy be dispensing?	No
If the source is not a FDA licensed facility, provide details regarding the purity, quality, stability and sterility of the investigational drug/biologic:	N/A - the source is an FDA licensed facility
Identify who will be preparing the investigational drug /biologic for administration and describe in detail how it will be prepared:	The BoNT-A will be prepared by a trained physician or nurse. Four syringes using 25 units of BoNT-A and 1 mL of normal saline will be prepared per limb.
Indication(s) under Investigation:	BoNT-A (trade name BOTOX, generic name onabotulinumtoxinA) is currently FDA approved for injection into extremity musculature for other medical conditions (i. e. muscular hypertrophy/spasticity). We are investigating its usage for chronic exertional compartment syndrome.
Where will the drug be stored	Within a locked cabinet in a Dept. of Physical Medicine & Rehabilitation procedure room
Drug Storage Restrictions (including temperature, etc.):	Unopened vials of BoNT-A (trade name BOTOX, generic name (onabotulinumtoxinA) will be stored in a refrigerator set for 2°C to 8°C or 36°F to 46°F.
Administration Instructions:	Standard aseptic technique will be followed. Insertion of the correct compartment will be accomplished using ultrasound guidance. The anterior and lateral compartment will be separated into thirds measuring from the tibial plateau to the head of the calcaneus. Injections will be given at approximately 1/3 the distance from the tibial plateau for the proximal injection and 2/3 the distance from the tibial plateau for the distal injection. Injections will only be given to compartments that have elevated pressures. If the lateral compartment is affected, the peroneus longus and brevis muscles will receive 25 units proximally and 25 units distally, for a total of 50 units, of BoNT-A. If the anterior compartment is affected, a total of 50 units of BoNT-A will be given: 25 units at the proximal region and 25 units at the distal region.
Possible Untoward Effects, Their Symptoms & Treatment:	The potential side effects for BoNT-A (trade name BOTOX, generic name onabotulinumtoxinA) include: rare minor side effects of bleeding, pain, infection, transient general muscle weakness and muscular atrophy, flu-like symptoms, and even rarer transient breathing and swallowing difficulties which has the potential to cause death if not appropriately treated.

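### Saline may be injected at as little as half the volume implied for each BoNT-A injection, although the plan describes the two as given in the same way

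*Combined protocol and SAP*

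**What the plan says.** Section 10.1, under BoNT-A Injections, specifies that "a solution of 25 units of Botulinum toxin, per 1 mL of normal saline will be used for each injection". It fixes the amount at each site. The anterior compartment gets "25 units to the proximal anterior compartment and 25 units to the distal anterior compartment", and for the other compartment, "If the lateral compartment is affected, a total of 50 units of botulinum toxin will be given", again split equally between a proximal and a distal site. Participants in these arms "will receive up to 2 injections per affected anterior and/or lateral compartment".

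Section 18.2 gives the preparation, in the same words for Botox and for Xeomin: "Four syringes using 25 units of BoNT-A and 1 mL of normal saline will be prepared per limb". The dose range is "50-100 units per limb".

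Section 10.1, under Saline Injections, says that the placebo is given "in the identical manner above, using the appropriate amount of solution (0.5 mL to 1 mL"). It adds that syringes are prepared "out of view of the participant to ensure appropriate blinding". It gives no rule for choosing a volume within the range.

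Section 9.4 calls the trial single-blinded. The Study Blinding text in Section 10.1 blinds only participants to saline or BoNT-A, until the 3-month visit is complete.

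**The concern.** A placebo injection should differ from the active one in the drug and in nothing else. Here the BoNT-A text leads to a single volume per injection, while the saline text gives a range whose lower end is half of it. Both cannot be the same procedure unless saline is always given at the top of its range, and nothing says that it is.

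What is at stake is the credibility of the blinded comparison of BoNT-A with saline: Group 3 v Group 1 and Group 4 v Group 2. Participants are unblinded after the 3-month visit, so only the 8-week and 3-month data are collected blind. Many of the outcomes in Section 10.2 rest on participant report or effort. These include UWRI, SANE, PSFS, GROC, pain, satisfaction, a self-paced run, and return to duty with pain that the patient judges tolerable. Such outcomes can shift if participants guess their arm.

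**Working it through.** **Inputs**
- BoNT-A concentration: 25 units per mL (Section 10.1).
- BoNT-A per site: 25 units, with a proximal and a distal site in each affected compartment (Section 10.1).
- Syringe preparation: 25 units and 1 mL, four syringes per limb (Section 18.2, both products).
- Saline: 0.5 to 1 mL (Section 10.1), read here as per injection. The sentence does not name the unit, but it follows a statement about how each injection is given.

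**Step 1: reproduce the plan's own dose range.** Units per limb = 25 × 2 sites × number of affected compartments.
- One compartment: 25 × 2 × 1 = 50 units.
- Two compartments: 25 × 2 × 2 = 100 units.

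This matches the range stated in Section 18.2, so the inputs are being read as the plan intends.

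**Step 2: BoNT-A volume per injection.** Volume = units ÷ concentration = 25 ÷ 25 = 1 mL. Section 18.2 gives the same figure directly, as 1 mL per syringe.

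**Step 3: volume per limb in each arm**

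| Affected compartments | Sites | BoNT-A | Saline | Saline as share of BoNT-A |
|---|---|---|---|---|
| 1 | 2 | 2 × 1 = 2 mL | 2 × 0.5 to 2 × 1 = 1 to 2 mL | 50% to 100% |
| 2 | 4 | 4 × 1 = 4 mL | 4 × 0.5 to 4 × 1 = 2 to 4 mL | 50% to 100% |

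**Step 4: does 0.5 mL correspond to any BoNT-A injection in the plan?** At the stated concentration, 0.5 mL would hold 0.5 × 25 = 12.5 units, and no passage describes such an injection. Putting 25 units into 0.5 mL would need 25 ÷ 0.5 = 50 units per mL, and no passage states that concentration. The lower saline bound has no BoNT-A counterpart. These two figures only test consistency; neither is a proposal.

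**Step 5: does the stated safeguard close the gap?** Preparing syringes out of sight hides the preparation. It does not make the injected volumes equal.

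**The case against.** The strongest reply is that the mismatch is permitted, not planned. The reference to an appropriate amount can fairly be read as meaning whatever matches the injection being replaced, followed by a loose parenthesis. Saline at 1 mL throughout would comply in full. Sameness of manner can also refer to site, ultrasound guidance and technique, and nothing contradicts it there. All of this stands. But if matching was meant, a range is the wrong way to say it, because only one value in it matches the BoNT-A preparation.

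The route to unblinding is also uncertain. Each participant is assigned to one arm and has no study injection of the other kind to compare with before 3 months. A smaller volume is informative only to someone who knows the BoNT-A volume, and the protocol does not say that participants are told it. This stands, and it limits the point to a possible threat of unknown size.

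Several stronger readings are tempting, and the documents do not support them:
- That staff who know the allocation choose the volume. Section 10.1 says who prepares the syringes, not who sets the volume. Because the design is single-blind, whoever prepares the saline probably knows that it is saline, but this is an inference.
- That participants will see or feel the difference. No passage addresses this.
- That the volume gap would alter compartment pressure and so the outcomes. Nothing in the documents indicates this. The first follow-up is at 8 weeks, and pressure is re-tested at 6 months.
- That Sections 10.1 and 18.2 disagree about BoNT-A. They agree on it. The conflict is between the saline sentence and the BoNT-A text in both sections.

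**Conclusion.** The inconsistency is real, and no other part of the documents resolves it. The BoNT-A text implies 1 mL per injection, while the saline text permits 0.5 to 1 mL with no rule for choosing. The gap can be anywhere from none to 50% of the BoNT-A volume, or up to 2 mL per limb when four sites are treated. The 50% is a ceiling on volume, reached only if every saline site is at the minimum. It is not a measure of bias.

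The conclusion assumes that the saline range applies per injection and that each 1 mL BoNT-A syringe is injected in full. Any effect on guessing the arm, and through it on Group 3 v Group 1 and Group 4 v Group 2 up to 3 months, cannot be computed from the documents. No significance level, power or sample size changes. The point is worth correcting because participant blinding is the only blinding described and the threat can be removed at almost no cost.

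**What to change.** Reconcile the BoNT-A and saline paragraphs of Section 10.1 with the preparation entries for both products in Section 18.2, so that the injected volume per site does not differ between the saline and BoNT-A arms. What that volume should be is for the sponsor's clinicians. The statistical requirement is only that it does not depend on the arm.

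The cost is a change of wording in Section 10.1 and in the preparation instructions. No procedure, visit or data item is added.
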